1.2 Background

In 2017 an estimated 8,900 Canadians will be diagnosed with bladder cancer¹. The mainstay of surgical treatment for muscle-invasive bladder cancer is radical cystectomy (RC) with lymph node dissection. Large prospective cohort studies suggest that at least 64% of patients undergoing RC experience at least one complication within 3 months^{2,3}. In an attempt to reduce

these complications and shorten length of hospital stay postoperatively, Rockyview General Hospital (RGH) is implementing a new enhanced recovery protocol (ERP) that will employ multidisciplinary, evidence-based clinical interventions, drawing upon the Enhanced Recovery After Surgery (ERAS) protocols⁴ for its development. ERAS protocols have been shown to reduce length of hospital stay and morbidity post-colorectal surgery, and provide an evidence-based, multidisciplinary approach to surgical care. It is unclear whether available evidence suggests ERPs facilitate earlier recovery of strength and function, and previous efforts to improve recovery have traditionally focused on the postoperative period, during which cancer patients may be fatigued, concerned about disturbing the healing process, or anxious as they await additional treatments for their underlying condition.⁵ Given this, the preoperative period may in fact be a more salient time to intervene. Optimizing an individual's functional capacity can begin during the waiting period before surgery as it capitalizes on the better physical health compared with the acute postoperative period^{6,7}. Moreover, interventions prior to surgery can potentially improve complication rates perioperatively. This process of enhancing an individual's functional capacity to withstand the stress of surgery is called prehabilitation⁸.

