4 STUDY DESIGN

4.1 Study Overview

This is a single center, single-blind, pragmatic randomized-control trial. There will be a total of 50 (fifty) participants in the study. Each participant will be randomly enrolled into a prehabilitation or no-prehabilitation group at time of consent for RC and those in the intervention group will undergo 8 weeks of prehabilitation through the Total Cardiology program, hosted through the Repsol Centre. Each participant, independent of study group assignment, will receive the standard treatment as outlined in the Enhanced Recovery Protocol (ERP) for Radical Cystectomies (see Appendix 1). Those enrolled in the prehabilitation group will attend 2 supervised exercise-based sessions per week and will complete a home-exercise program three times per week (total 5 exercise sessions per week). In addition, they will receive 5 protein supplement drinks per week to consume after exercise, and will attend classes on nutrition and stress/anxiety reduction techniques. Measurements will be taken at baseline, 6 weeks (as a part of their regularly scheduled pre-admission clinic appointment), 8 weeks (just prior to surgery), 4 weeks post-op, and 8 weeks post-op.

Those patients enrolled in the no-prehabilitation group will receive a general, unsupervised, home-exercise program, information regarding good nutrition. They will be followed at their regularly scheduled appointments. Again, measurements will be taken at the same time intervals as the prehabilitation group.

Screening data will be reviewed to determine subject eligibility. Subjects who meet all inclusion criteria and none of the exclusion criteria will be entered into the study.

The following treatment groups will be established:

- Standard ERP + Trimodal Prehabilitation
- Standard ERP

Total duration of subject participation will be approximately sixteen weeks. Total duration of the study is expected to be approximately 1.5 years.

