5.4 Blinding

Due to the nature of the study, we are unable to conceal to the research staff or participants from the different aspects of trimodal prehabilitation. However, all research data will be coded with anonymous unique identifiers so statistical analysis is performed blinded and without bias. The assessor-blinded data will not be broken on completion of the clinical study.

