6.3 Physical Examination

Physical examinations are completed as a regular part of their pre-surgical care. During the participant's visit to the preadmission clinic (PAC), 2 weeks prior to surgery, they will undergo medical screening by an Internist and Anaesthesiologist as standard practice. Qualified staff (physician assistant, nurse, and physiotherapist) may complete an abbreviated physical exam at all other visits as part of standard practice. New abnormal physical exam findings will be documented and the participant will be referred to a physician for further examination.

Prior to the commencement of their prehabilitation program, participants undergo a medical screening exam at the Total Cardiology facility to ensure patients are medically stable.

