7 EVALUATIONS BY VISIT

7.1 Visit 1 (Baseline / Surgical consent)

1. Review the study with the subject and obtain written informed consent (Appendix 5).
2. Assign the subject a unique screening number.
3. Record demographics data.
4. Record Charlson Comorbidity Index.
5. Record chemotherapy history and schedule for ongoing treatments.
6. Record vital signs.
7. Collect functional outcome measures (as listed above).
8. Perform and record incentive spirometry.
9. Randomize subject into treatment or control group.
10. If subject is selected for treatment group, schedule subject for commencement of trimodal prehabilitation with the Total Cardiology program. If selected for control group, subject will be given a home-exercise program and nutrition information as described above.
11. Explain how to complete the study journal (exercise & nutrition compliance).
12. Explain how to complete the online 24-hr food recall.
13. Complete baseline subjective questionnaires (as listed above).

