7.2 Visit 2 (Pre-admission Clinic appointment)

1. Record any adverse events and review subject diary for adverse events/compliance.
2. Reinforce home based program and review of postoperative pathway.
3. Perform and record incentive spirometry.

4. Blood work (haematology and blood chemistry profile) completed as a part of their pre-admission screening with internal medicine. No additional blood tests will be requested for study purposes.

*Note: If after review by the medical team the patient is determined to be a poor candidate for surgery, participant will be withdrawn from the study at this point.

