8 DISCONTINUATION/WITHDRAWAL OF SUBJECTS

8.1 Early discontinuation and/or withdrawal of subjects from trimodal prehabilitation

A subject may be discontinued from study treatment at any time if the subject, the investigator, or the primary medical team feels that it is not in the subject's best interest to continue. The following is a list of possible reasons for study treatment discontinuation:

- Subject withdrawal of consent
- Subject is not compliant with study procedures
- Adverse event that in the opinion of the investigator would be in the best interest of the subject to discontinue study treatment
- Protocol violation requiring discontinuation of study treatment
- Lost to follow-up
- Sponsor request for early termination of study

If a subject is withdrawn from treatment due to an adverse event, the subject will be followed and treated by their primary medical team until the abnormal parameters or symptoms have resolved or stabilized.

Subjects are free to withdraw from participation at any time, for any reason, specified or unspecified, and without prejudice. A subject may also withdraw their personal study data and in this case, all relevant recorded data will be securely erased, along with any paper files shredded, and the data will be excluded from analysis. This can be done up to the time when the report on study findings is finalized and distributed.

Reasonable attempts will be made by the investigator to provide a reason for subject withdrawals. The reason for the subject's withdrawal from the study will be specified in the subject's source documents.

Subjects who withdraw from the study will not be replaced.

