9 STATISTICAL METHODS AND CONSIDERATIONS

9.1 Quantitative Analysis

An available case analysis without imputation of missing values will be conducted. All analyses will be performed using Stata 14.1 (2015, StataCorp). All continuous variables will be reported as mean, 95% confidence interval. Categorical variables will be presented as frequency (%) and compared using Pearson's χ^2 test. A mixed effects model will be used to analyze repeated measures, including our primary outcome the 6MWT, because this method had advantages in dealing with missing data and controlling for baseline variables. A P-value <0.05 will be considered statistically significant.

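### Section 7.2 withdraws from the study, about six weeks after randomisation, patients judged poor surgical candidates; they should stay in follow-up and be accounted for by arm

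*Protocol*

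**What the plan says.** - **Randomisation.** Protocol section 7.1 places it at Visit 1: "Randomize subject into treatment or control group".
- **Timing of Visit 2.** Section 4.1 gives the schedule as "Measurements will be taken at baseline, 6 weeks (as a part of their regularly scheduled pre-admission clinic appointment), 8 weeks (just prior to surgery"). Section 6.3 agrees on the clinic visit: "2 weeks prior to surgery, they will undergo medical screening by an Internist and Anaesthesiologist as standard practice".
- **The rule.** The note closing section 7.2 says that, if after medical review the patient is "determined to be a poor candidate for surgery, participant will be withdrawn from the study at this point".
- **Aim of the intervention.** Section 1.2 describes enhancing a person's "functional capacity to withstand the stress of surgery is called prehabilitation". Section 2 gives the same rationale.
- **Blinding.** Section 5.4 says "we are unable to conceal to the research staff or participants". Only the statistical analysis is described as blinded.
- **Analysis.** Section 9.1: "An available case analysis without imputation of missing values will be conducted". A mixed effects model is named for the 6MWT, chosen partly because it can control for baseline variables. Section 8.1 adds that withdrawn subjects are not replaced.
- **Stopping the programme.** Section 8.1 lists reasons for discontinuing study treatment, among them "Subject is not compliant with study procedures". It does not say whether Visits 3 to 5 continue afterwards.

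**The concern.** Leaving the study depends on a judgement made after randomisation about an attribute the intervention is designed to change. Nothing in the protocol conceals the arm from those who make that judgement. If prehabilitation makes some borderline patients operable, the patients who remain may differ between arms in ways that randomisation did not produce.

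The rule also ends study participation, which goes further than not operating. The Visit 3 functional tests are lost, although they could be done without surgery. No section asks for the number not proceeding to surgery by arm, and it is not among the clinical outcomes in section 6.9. For a pilot that also wants to learn who benefits most from prehabilitation (section 3.3), that number matters.

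**Working it through.** **1. Timing.** The programme lasts 8 weeks and the clinic visit is 2 weeks before surgery: 8 − 2 = 6 weeks after baseline, as section 4.1 states. The removal is after randomisation and well into the programme.

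**2. What data a withdrawn patient has.** Section 4.1 speaks of measurements at 6 weeks, but the Visit 2 list in section 7.2 contains only adverse events, diary review, reinforcement of the home programme, incentive spirometry and blood work. The schedule in section 1.1 names baseline, day of surgery, and weeks 4 and 8 after surgery. On the visit lists, a patient withdrawn at Visit 2 therefore has one 6MWT, at baseline.

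**3. What the model does with it.** If baseline is a covariate, a patient with no later 6MWT drops out. If baseline is one of the repeated outcomes, the patient informs the baseline mean and essentially nothing in the treatment contrast. Either way the result relies on missingness at random given the recorded 6MWT, and Visit 2 fitness is not recorded by any 6MWT.

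**4. How large a bias could be.** The protocol has no power calculation or variance figure to reproduce; 25 + 25 = 50 comes from funding. Everything below is therefore assumption, with no true treatment effect. If the lowest share q of an arm on a normal selection variable is removed, the mean of those remaining is λ(q) = φ(z_q)/(1 − q) SD. With correlation ρ to the week-8 6MWT, the unadjusted bias is ρ[λ(q_T) − λ(q_C)], where T is prehabilitation and C is control.

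*Selection on baseline 6MWT, ρ = 0.7:*

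| Analysis | 10% control v 2% prehabilitation | 15% v 5% |
|---|---|---|
| Unadjusted week-8 mean | 0.7 × (0.0494 − 0.1950) = −0.102 SD | 0.7 × (0.1086 − 0.2743) = −0.116 SD |
| Adjusted for baseline | 0 | 0 |
| Change from baseline, equal SDs | −0.3 × (0.0494 − 0.1950) = +0.04 SD | −0.3 × (0.1086 − 0.2743) = +0.05 SD |

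The factor −0.3 is ρ − 1. The same removals give a negative, zero or positive bias depending on the analysis.

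*Selection on Visit 2 fitness, unadjusted, ρ from 0.3 to 0.7:*

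| Control v prehabilitation withdrawn (of 25) | Bias |
|---|---|
| 4% v 4% (1 v 1) | 0 |
| 8% v 4% (2 v 1) | −0.02 to −0.05 SD |
| 12% v 4% (3 v 1) | −0.04 to −0.10 SD |
| 12% v about 0% (3 v 0) | −0.07 to −0.16 SD |

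Baseline adjustment would remove the part of these figures that runs through baseline, so they are not estimates for the planned model.

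**5. Scale.** With 24 and 22 patients, the standard error of a difference is √(1/24 + 1/22) = 0.295 SD. A bias of 0.10 SD would be about a third of that and would move a nominal two-sided 5% test to about 6.3%. The difference detectable with 80% power rises from (1.96 + 0.84) × √(2/25) = 0.79 SD with 25 per arm to 0.85 SD with 22.

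**The case against.** **Some loss is unavoidable.** A patient who is not operated on has no post-operative 6MWT, whatever section 7.2 says. This stands. The avoidable part is the lost Visit 3 measurement and the missing account of who did not reach surgery.

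**The planned model controls for baseline.** This stands and matters. A reader might infer a bias of about a tenth of an SD against prehabilitation. The documents do not support that figure: it is an unadjusted difference with assumed rates, it vanishes on adjustment if baseline 6MWT is the selecting variable, and it changes sign for change from baseline. Direction is open for another reason too: section 4.6 gives patients selected for prehabilitation further exercise testing, which could reveal more unfit patients in that arm.

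**Removals may be rare.** Patients have already consented to surgery, and section 4.4 excludes ASA class 4–5, severe cardiac abnormality and end-stage organ disease. This stands as a limit on size.

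**The SAP may handle it.** It may well define analysis sets and estimands. It cannot recover measurements that the protocol tells staff not to take.

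**Two further inferences go too far.** A reader might take section 5.4 to mean that those judging fitness know the arm. It names research staff and participants, while section 7.2 refers to the medical team; the protocol is silent on whether that team knows. A reader might also take section 8.1 to remove non-compliers from the study. Its heading and list concern stopping the programme, and data are excluded only when a subject withdraws their own data. Because the list also includes loss to follow-up and withdrawal of consent, which normally end follow-up, the wording is ambiguous, but it does not set up a second exclusion.

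**Conclusion.** The point holds in limited form. Section 7.2 creates an avoidable exclusion after randomisation, on an attribute the intervention is meant to influence, and the available-case mixed model cannot repair it for patients with only a baseline 6MWT. Bias arises only if removal differs between arms on fitness that baseline 6MWT does not capture. Its size and sign cannot be determined from the protocol. It is absent if nobody is withdrawn or if selection acts only through the adjusted baseline, and in the simple model above also if equal shares are removed under the same cut. The figures in the working show that a handful of patients could matter a little; they do not predict what will happen. Severity is minor to moderate. Who should have surgery is not in question.

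**What to change.** Leave the surgical decision to the clinical team and change only follow-up, reporting and analysis.

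1. In section 7.2, replace the instruction to withdraw from the study with wording to this effect: *the participant remains in the study; functional measures are taken at the planned Visit 3 date where possible; all collected data are analysed in the allocated arm.*
2. Report by arm the number and proportion not proceeding to surgery.
3. State that the post-operative 6MWT comparison is conditional on having had surgery. This needs saying because a mixed model given a Visit 3 value would otherwise implicitly predict a post-operative result for someone who had no operation.
4. In section 8.1, clarify that stopping the programme does not by itself end Visits 3 to 5. The participant's right to withdraw, and to withdraw their own data, is unchanged.

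Scoring unoperated patients as not having returned to function is debatable, since they had no operation to recover from, and is not required here.

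The cost is a short amendment and a few extra assessments with tests already in use. The change makes the pre-operative comparison more complete and the path to surgery visible; it cannot supply a post-operative 6MWT for patients who are not operated on.

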7.3 Visit 3 (Pre-operative, day of surgery)

1. Record any adverse events and review subject diary for adverse events/compliance.
2. Perform and record incentive spirometry.
3. Perform and record functional outcome measures as listed above.

7.4 Visit 4 (Post-operative follow-up appointment at 4 weeks)

1. Perform and record incentive spirometry.
2. Perform and record functional outcome measures as listed above.
3. Record participant's self-reported exercise post-operatively.

7.5 Visit 5 (Post-operative follow-up appointment at 8 weeks)

1. Perform and record incentive spirometry.
2. Perform and record functional outcome measures as listed above.
3. Record participant's self-reported exercises post-operatively.
4. Complete subjective questionnaires as listed above.

7.6 Visit 6 (Interviews)

1. Interested participants (n=8) will be invited to participate in individual interviews, which will last up to 75 min. The interviews will be carried out by a PaCER trained researcher (CG).
2. An amendment will be submitted for this ethics proposal which details the nature of the interviews.

8 DISCONTINUATION/WITHDRAWAL OF SUBJECTS

8.1 Early discontinuation and/or withdrawal of subjects from trimodal prehabilitation

A subject may be discontinued from study treatment at any time if the subject, the investigator, or the primary medical team feels that it is not in the subject's best interest to continue. The following is a list of possible reasons for study treatment discontinuation:

- Subject withdrawal of consent
- Subject is not compliant with study procedures
- Adverse event that in the opinion of the investigator would be in the best interest of the subject to discontinue study treatment
- Protocol violation requiring discontinuation of study treatment
- Lost to follow-up
- Sponsor request for early termination of study

If a subject is withdrawn from treatment due to an adverse event, the subject will be followed and treated by their primary medical team until the abnormal parameters or symptoms have resolved or stabilized.

Subjects are free to withdraw from participation at any time, for any reason, specified or unspecified, and without prejudice. A subject may also withdraw their personal study data and in this case, all relevant recorded data will be securely erased, along with any paper files shredded, and the data will be excluded from analysis. This can be done up to the time when the report on study findings is finalized and distributed.

Reasonable attempts will be made by the investigator to provide a reason for subject withdrawals. The reason for the subject's withdrawal from the study will be specified in the subject's source documents.

Subjects who withdraw from the study will not be replaced.

9 STATISTICAL METHODS AND CONSIDERATIONS

9.1 Quantitative Analysis

An available case analysis without imputation of missing values will be conducted. All analyses will be performed using Stata 14.1 (2015, StataCorp). All continuous variables will be reported as mean, 95% confidence interval. Categorical variables will be presented as frequency (%) and compared using Pearson's χ^2 test. A mixed effects model will be used to analyze repeated measures, including our primary outcome the 6MWT, because this method had advantages in dealing with missing data and controlling for baseline variables. A P-value <0.05 will be considered statistically significant.

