1 INTRODUCTION

1.1 Abstract

A trimodal preoperative intervention known as prehabilitation (involving exercise, nutrition and psychological care) has been found to successfully improve functional recovery, an important patient-centered outcome, in colorectal surgery patients following the Enhanced Recovery After Surgery (ERAS) pathway. It is unknown whether the same program will be effective in patients undergoing surgery for bladder cancer (cystectomy). It is an opportune time to study prehabilitation at the Rockyview General Hospital given the recent roll-out of the Enhanced Recovery Protocol (ERP) for cystectomy patients and ongoing implementation of an integrated prehabilitation program.

Objective: To evaluate the appropriateness of a standardized prehabilitation program for implementation into an ERP for cystectomy patients and determine whether prehabilitation facilitates earlier recovery of functional capacity, as measured by six-minute walk test (6MWT)

Hypothesis: Prehabilitation will ultimately improve recovery of functional capacity, clinical and patient-centered outcomes in patients undergoing radical cystectomy for bladder cancer.

Design: A pragmatic randomized control trial of radical cystectomy patients following ERP and an 8-week trimodal prehabilitation program consisting of exercise therapy combined with nutritional counselling, protein supplementation, and psychological care will be compared to a cohort of patients following ERP care alone.

Main Outcome Measures: Return to preoperative functional walking capacity, as assessed using the validated six-minute walk test at the 8th postoperative week. All measures will be recorded at baseline, the day of surgery, and four and eight weeks after surgery. Traditional clinical outcome measures (e.g., length of hospital stay) will also be evaluated. Finally, patient interviews will be conducted to evaluate the appropriateness of prehabilitation.

Conclusion: The proposal will provide insight into the feasibility and effectiveness of trimodal prehabilitation for radical cystectomy patients and ultimately lead to improved clinical outcomes and reduced morbidity.

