4.5 Total Number of Participants and Sample Size Justification

A total of 50 participants who meet the inclusion criteria and are willing to participate in the study will be enrolled, with 25 participants randomly allocated to each study treatment group. As this is a pilot study, we have funding for at most 25 participants to undergo prehabilitation.

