6.7 Functional Outcomes

A number of functional outcome measures will be utilized to help determine which measures represent a valid index of recovery and are sensitive to change in our post-surgical candidates.

a. 6-minute walk test (6MWT)

The 6MWT is an exercise test used to assess aerobic capacity and to a secondary extent, functional mobility. It is a standardized test that has been validated for a variety of populations and can be useful in monitoring a person's capacity to ambulate²⁰. Briefly, the 6MWT requires the participant to ambulate for 6 continuous minutes on a 30m track with a goal of ambulating as far as they can manage in the 6 minutes. The total distance ambulated is then recorded.

b. 10m walk test (10mWT)

In contrast to the 6MWT, the 10mWT takes place by having the participant ambulate a total of 10 meters at their preferred walking speed. The time it takes to ambulate the 10m is then measured and recorded. Walking speed standards have been well established in literature and are predictive of poor health outcomes.^{21,22}

c. 30s sit-to-stand test (30s STS)

The 30s STS test is well validated for a number of conditions and age groups and correlates with lower extremity strength and function. The test requires the participant to complete as many sit-to-stand movements as possible in 30 seconds. The number of stands is then recorded.

d. Hand-grip dynamometer

A hand-grip dynamometer allows for the measurement of various types of grip strength. Grip strength has been shown to be a predictor for upper extremity strength and function, and even as a predictor for ability to carry out activities of daily living²³. For this reason, hand-grip dynamometry allows for a simple objective measure of upper extremity function.

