9.2 Power & Sample Size

Power and sample size are limited by the amount of funding available. The grant amount of \$15,000 allows for a total of ~50 patients with 25 being enrolled in the prehabilitation group.

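### The available-case rule leaves patients who died or were too ill to walk out of week-8 return to walking capacity, and it can bias the 6MWT difference if such losses differ by arm

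*Protocol*

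**What the plan says.** Section 9.1 of the Protocol sets the rule for missing data: "An available case analysis without imputation of missing values will be conducted". For the primary outcome it continues: "A mixed effects model will be used to analyze repeated measures, including our primary outcome the 6MWT, because this method had advantages in dealing with". The benefits it goes on to claim are the handling of absent observations and adjustment for baseline.

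Section 1.1 words the main outcome as "Return to preoperative functional walking capacity, as assessed using the validated six-minute walk test at the 8th postoperative week". Section 6.7 describes the test score only as a distance: "The total distance ambulated is then recorded". On timing, section 1.1 says: "All measures will be recorded at baseline, the day of surgery, and four and eight weeks after surgery". Section 1.2 reports that "at least 64% of patients undergoing RC experience at least one complication within 3 months", a window that contains both postoperative tests.

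The Protocol does not say how a patient who has died, or who cannot attempt the walk, is counted at week 4 or 8. It names no sensitivity analysis of the missing-data assumption. Section 8.1 asks for the reason for withdrawal from the study, but sections 7.4 and 7.5 ask for no reason when a single walk is missed.

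**The concern.** An available-case rule is harmless when the reason for a missed measurement has nothing to do with its value, given what has been observed. After cystectomy one obvious reason for a missed walk is poor function itself. A patient who misses both postoperative tests through illness contributes only preoperative distances, and these do not show the postoperative decline. The mixed model then fills the gap as if the patient had recovered like others with similar preoperative walks.

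Two results are exposed. For return to capacity, a patient who is dead or too ill to walk at week 8 has not returned, yet the rule removes that patient from the denominator. For mean distance, each arm's week-8 level is set too high, by more in the arm that loses more patients. The trial hopes that prehabilitation will reduce morbidity, so losses may differ by arm as a consequence of treatment.

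This concerns a rule that the Protocol states. It is not a detail merely left for a later plan.

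**Working it through.** **What can be reproduced.** The Protocol gives no SD, effect size, visit correlation, or rate of death or inability to walk. Section 9.2 explains the sample size by money: "Power and sample size are limited by the amount of funding available". There is no stated figure to reproduce. Apart from the 25 per arm in section 4.5, the inputs below are assumptions.

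**1. Return to capacity.** Let r be the proportion returned among those tested and m the share dead or too ill to walk. The proportion of the whole arm that has returned is r(1 − m), so the available-case figure is too high by r·m.

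- r = 60%, m = 12%: 0.60 × 0.88 = 52.8%, an overstatement of 7.2 points.
- Over r from 40% to 80% and m from 4% to 20%: from 0.40 × 0.04 = 1.6 points to 0.80 × 0.20 = 16 points.

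The difference between arms shifts too. Take 40% (control) and 80% (prehabilitation) among those tested, an apparent gap of 40 points:

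| Lost, control / prehabilitation | Returned, whole arm | Gap |
|---|---|---|
| 12% / 12% | 35.2% / 70.4% | 35.2 points |
| 20% / 8% | 32.0% / 73.6% | 41.6 points |
| 8% / 20% | 36.8% / 64.0% | 27.2 points |

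**2. Mean distance under the mixed model.** Assume normal distances, SD 90 m, correlation ρ = 0.7 between visits and a true week-8 difference of 20 m. The lowest fraction m of week-8 walkers is unmeasured at weeks 4 and 8, so the model has only the two preoperative walks for them.

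- Share of week-8 variance explained by two preoperative walks: R² = 2ρ²/(1 + ρ) = 0.98/1.70 = 0.576.
- With z = Φ⁻¹(m): λ = φ(z)/(1 − m), and the variance ratio among those tested is k = 1 + zλ − λ².
- Upward bias of the arm mean under missing at random: 90 × λ × (1 − R²)/(1 − R² + R²k).

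For m = 20%: z = −0.842, λ = 0.350, k = 0.583. The last factor is 0.424/(0.424 + 0.576 × 0.583) = 0.558, and the bias is 90 × 0.350 × 0.558 = 17.6 m.

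For m = 8%: z = −1.405, λ = 0.162, k = 0.747, factor 0.496, bias 7.2 m.

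The same formula gives 8.9 m at 10%, 10.6 m at 12%, 13.2 m at 15% and 22.1 m at 25%. The estimated difference is 20 + bias(prehabilitation) − bias(control):

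| Lost, control / prehabilitation | Estimate (true 20 m) |
|---|---|
| 20% / 8% | about 10 m |
| 25% / 8% | about 5 m |
| 15% / 10% | about 16 m |
| 12% / 12% | 20 m |
| 8% / 20% | about 30 m |

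Simulations on the same SD, correlation and true difference, with somewhat different modelling choices, gave about 12 m at 20%/8% and about 28 m at 8%/20%.

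A separate simulation used SD 100 m, visit correlations of 0.6 to 0.8, a true difference of about 30 m and a looser link between illness and distance. It gave 21 m at 20%/8% and 40 m at 8%/20%. With 10% lost in each arm the difference stayed near 30 m, but both means were about 8 m too high.

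**3. Scale in this trial.** Section 4.5 gives 50 patients, "with 25 participants randomly allocated to each study treatment group". So 20% against 8% is 5 patients against 2. If both arms truly lose 12%, independent binomial counts differ by three or more in about 27% of trials (18% at a rate of 8%, 32% at 15%). The baseline-adjusted standard error with complete data is 90 × √(1 − 0.49) × √(2/25) = 18 m, so a bias of about 10 m is a little over half a standard error.

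**The case against.** The best defence has four parts.

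- **The mixed model is a reasonable main analysis.** It uses all observed walks and softens the bias. This stands, and the fix keeps it.
- **The text is silent on these patients; it does not expressly exclude them.** No cut-off for return is given. A patient known to have died could be classed as not returned without any imputation, and one who attends but cannot walk could be recorded as 0 m. This is fair, but section 9.1 states only the available-case rule, and nothing in the Protocol directs either treatment. Read as written, a patient with no week-8 distance drops out.
- **Reason codes and sensitivity analyses are often left to an analysis plan.** This is true of the reason code taken alone. Section 8.1 partly covers it, and sections 6.9 and 10.1 collect complications and readmissions separately. The counting rule is different, because it qualifies a rule that the Protocol states.
- **The size rests on assumptions.** The 64% in section 1.2 is any complication within three months; it is not inability to walk at week 8. Section 4.4 excludes the least fit patients. Removing the lowest walkers at both postoperative visits is close to a worst case. All of this stands.

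A reader might infer that return is overstated in both arms, or that the benefit of prehabilitation is bound to be understated. The documents support neither. The first needs at least one such patient in each arm. The second needs more such losses among controls, and the bias reverses if prehabilitation loses more.

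**Conclusion.** The point holds in conditional form. For return to capacity at week 8, the stated rule overstates return in any arm with patients who are dead or too ill to walk, by r·m; this is arithmetic, and only r and m are unknown. For mean 6MWT, the mixed-model difference is nearly unbiased when such losses are equal, and can be wrong in either direction when they are not.

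The illustrative size is 8 to 10 m either way on a true 20 m for a 20% against 8% imbalance. That rests on SD 90 m, correlation 0.7 and strongly function-related losses, none of which comes from the Protocol. At about half a standard error it is unlikely to decide this trial alone. It still matters because section 2 intends the results to form the basis for multi-site studies, and a distorted effect or return rate would carry forward.

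**What to change.** Keep the mixed model as the main analysis and add to section 9.1:

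1. Patients who have died, or who cannot walk because of illness, at week 8 count as not returned in the return-to-capacity outcome.
2. One pre-specified sensitivity analysis of week-8 6MWT is run, either rank-based with these patients ranked worst or delta-adjusted.
3. In support of both, the reason for each missed walk (died, too ill to walk, other) is recorded at the visit.

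The cost is one form field and one extra analysis. A worst-rank result is harder to express in metres. The reason for a missed walk may be hard to recover later, so the field should be in place before postoperative visits begin.
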